5.1.4 Complementary Output

Additional subgroup analyses by number of years ($3 \leqslant$ years < 4 , $4 \leqslant$ years < 5 , $5 \leqslant$ years $\leqslant 6$) elapsed since priming vaccination received in either clinical studies MET50, MET43, or outside of Sanofi Pasteur trials, age group (13 to 17 years and 18 to 26 years), gender (Female and Male), and race (White, Asian, Black or African American, and Other) will be provided in Appendix 15 of the CSR.

Demographics analyses by number of years since primed vaccines only:

- Baseline demographics – All Randomized or Assigned Subjects
- Baseline demographics – Per-Protocol Analysis Set 1
- Baseline demographics – Per-Protocol Analysis Set 2
- Baseline demographics – Safety Analysis Set

Immunogenicity analyses (tables and figures):

- hSBA GMTs and 95% CI at D0 and D30 for each group – Per-Protocol Analysis Set 2
- hSBA GMTs and 95% CI at D0 and D06 for Groups 1 and 2 – Per-Protocol Analysis Set 1
- Vaccine seroresponse against meningococcal serogroups A, C, Y, and W measured by hSBA and 95% CI at D30 for each group – Per-Protocol Analysis Set 2
- Vaccine seroresponse against meningococcal serogroups A, C, Y, and W measured by hSBA and 95% CI at D06 for Groups 1 and 2 – Per-Protocol Analysis Set 1
- hSBA titer $\geq 1:4$ and $\geq 1:8$ (vaccine seroprotection) against meningococcal serogroups A, C, Y, and W and 95% CI at D0 and D30 for each group – Per-Protocol Analysis Set 2
- hSBA titer $\geq 1:4$ and $\geq 1:8$ (vaccine seroprotection) against meningococcal serogroups A, C, Y, and W and 95% CI at D0 and D06 for Groups 1 and 2 – Per-Protocol Analysis Set 1
- rSBA GMTs and 95% CI at D0 and D30 for Groups 1 and 2 – Per-Protocol Analysis Set 2
- Vaccine seroresponse against meningococcal serogroups A, C, Y, and W measured by rSBA and 95% CI at D30 for Groups 1 and 2 – Per-Protocol Analysis Set 2
- rSBA titer $\geq 1:8$ and $\geq 1:128$ against meningococcal serogroups A, C, Y, and W and 95% CI at D0 and D30 in Groups 1 and 2 – Per-Protocol Analysis Set 2

Safety analyses:

Safety overview after injection – Safety Analysis Set

Analysis to assess the impact of COVID-19:

- To summarize the impact of COVID-19 on the overall study conduct
 - Early termination due to COVID-19
 - Impact on visit conduct (visit not done, partially done, data collection method/procedure change)
 - Major and critical protocol deviations due to COVID-19
- To identify and focus on the subset of subjects that were impacted by COVID-19
 - Defined as the subjects with at least one major/critical protocol deviation due to COVID-19 or who did not complete the study due to COVID-19 or who reported “VISIT NOT DONE” for safety follow up in pandemic form: The intention is to consider only relevant impacts on subjects (minor protocol deviations are not taken into account)
 - To summarize disposition across study visits for these subjects

- To provide an individual listing of these subjects and how they were impacted
- To assess the potential impact of COVID on treatment effect by replicating the tables addressing the primary immunogenicity and main safety endpoints in the subsets of impacted / non-impacted subjects

5.2 Analysis Sets

Five analysis sets will be used: the Full Analysis Set (FAS1 for D06, FAS2 for D30, and FAS3 for antibody persistence analyses), the Per-Protocol Analysis Sets (PPAS1 for D06 and PPAS2 for D30), and the Safety Analysis Set (SafAS).

5.2.1 Full Analysis Set

5.2.1.1 Full Analysis Set 1 and Full Analysis Set 2

The FAS is defined as the subset of subjects who received at least 1 dose of the study vaccine and had a valid post-vaccination serology result. Two FASs will be defined (FAS1 for D06 and FAS2 for D30). All subjects will be analyzed according to the treatment group to which they were randomized or assigned.

5.2.1.2 Full Analysis Set 3

The FAS3 is defined as a subset of subjects who had a valid pre-vaccination serology result for antibody persistence analyses.

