The persistence of antibodies against meningococcus has been studied in individuals that have received quadrivalent meningococcal conjugated vaccines, and the results have revealed that immunity wanes over time. Vaccine effectiveness for Menactra vaccine was 82% (CI = 54% to 93%) for adolescents vaccinated < 1 year earlier, 80% (CI = 52% to 92%) for adolescents vaccinated 1 to < 2 years earlier, 71% (CI = 34% to 87%) for adolescents vaccinated 2 to < 3 years earlier, and 59% (CI = 5% to 83%) for adolescents vaccinated 3 to < 6 years earlier (29). In October 2010, the Advisory Committee on Immunization Practices (ACIP) of the US Centers for Disease Control and Prevention (CDC) approved updated recommendations to include a booster dose of MCV4 at age 16 years for adolescents previously vaccinated at 11 to 12 years of age. For adolescents vaccinated at age 13 through 15 years, administration of a one-time booster dose is recommended, preferably at age 16 through 18 years. For those who are vaccinated with a primary dose of MCV4 at or after age 16 years, a booster dose is not recommended. The minimum interval between the first and booster dose recommended is 8 weeks (30).

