5.2.5 Exclusion Criteria

An individual fulfilling any of the following criteria is to be excluded from study enrollment:

1. Subject is pregnant, or lactating, or of childbearing potential and not using an effective method of contraception or abstinence from at least 4 weeks prior to the first vaccination until at least 4 weeks after the last vaccination. To be considered of non-childbearing potential, a female must be pre-menarche, or post-menopausal for at least 1 year, or surgically sterile.
2. Participation in the 4 weeks preceding the trial vaccination or planned participation during the present trial period in another clinical trial investigating a vaccine, drug, medical device, or medical procedure
3. Receipt of any vaccine in the 4 weeks (28 days) preceding the trial vaccination or planned receipt of any vaccine before D30 except for influenza vaccination, which may be received at least 2 weeks before study investigational vaccine.

4. Receipt of immune globulins, blood or blood-derived products in the past 3 months
5. Receipt of any meningococcal vaccine including a licensed or investigational MenACWY vaccine or MenB vaccine since participation in study MET50 or MET43
6. Menveo vaccine-primed subjects only (enrichment group for Group 2): receipt of more than 1 dose of Menveo vaccine or vaccination with another licensed or investigational MenACWY vaccine or with a licensed or investigational MenB vaccine
7. Known or suspected congenital or acquired immunodeficiency; or receipt of immunosuppressive therapy, such as anti-cancer chemotherapy or radiation therapy, within the preceding 6 months; or long-term systemic corticosteroid therapy (prednisone or equivalent for more than 2 consecutive weeks within the past 3 months)
8. History of meningococcal infection, confirmed either clinically, serologically, or microbiologically.
9. At high risk for meningococcal infection during the trial (specifically but not limited to subjects with persistent complement deficiency, with anatomic or functional asplenia, or subjects travelling to countries with high endemic or epidemic disease)
10. Known systemic hypersensitivity to any of the vaccine components, or history of a life-threatening reaction to the vaccines used in the trial or to a vaccine containing any of the same substances
11. Personal history of Guillain-Barré syndrome (GBS)

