12. Personal history of an Arthus-like reaction after vaccination with a tetanus toxoid-containing vaccine within at least 10 years of the proposed study vaccination
13. Verbal report of thrombocytopenia, contraindicating intramuscular vaccination
14. Bleeding disorder, or receipt of anticoagulants in the 3 weeks preceding inclusion, contraindicating intramuscular vaccination
15. Deprived of freedom by an administrative or court order, or in an emergency setting, or hospitalized involuntarily
16. Current alcohol abuse or drug addiction
17. Chronic illness (eg, HIV, hepatitis B, hepatitis C) that, in the opinion of the Investigator, is at a stage where it might interfere with trial conduct or completion
18. Moderate or severe acute illness/infection (according to Investigator judgment) on the day of vaccination or febrile illness (temperature $\geq 100.4^{\circ}\text{F}$). A prospective subject should not be included in the study until the condition has resolved or the febrile event has subsided
19. Receipt of oral or injectable antibiotic therapy within 72 hours prior to the first blood draw
20. Identified as an Investigator or employee of the Investigator or study center with direct involvement in the proposed study, or identified as an immediate family member (ie, parent, spouse, natural or adopted child) of the Investigator or employee with direct involvement in the proposed study

If the subject has a primary physician who is not the Investigator, the site must contact this physician with the subject's / subject's parents' / guardians' consent to inform him / her of the subject's participation in the study. In addition, the site should ask this primary physician to verify exclusion criteria relating to previous therapies, such as receipt of blood products or previous vaccines.

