- Influenza and other non-study vaccines: Influenza vaccine in the 2 weeks (14 days) preceding the trial vaccination up to the last blood draw and any other vaccines (other than the study vaccine) in the 4 weeks preceding the trial vaccination up to the last blood draw
- Immune globulins, blood or blood-derived products: used in the 3 months preceding the first blood draw and up to the last blood draw
- Immunosuppressive therapy such as immune-suppressors, immune-modulators with immunosuppressive properties, long-term systemic corticosteroids therapy (prednisone or equivalent for more than 2 consecutive weeks) within past 3 months, anti-cancer chemotherapy, anti-proliferative drugs such as DNA synthesis inhibitors, or radiation therapy: used in the 6 months preceding the first trial vaccination, and up to the last blood draw.
 - Category 2 medications will be reported in the CRB according to the collection period detailed above up to the last blood draw.

3) Category 3: Systemic (Oral or injectable) antibiotics, as they may interfere with bioassays used for antibody testing when taken before a blood draw.

- Category 3 medications will be reported in the CRB for the period of 3 days (72 hours) before each blood draw.

Note: Topical antibiotics (Inhaled, otic, ophthalmic, nasal, etc.) should not be captured or reported.

The information reported in the CRB for each reported medication will be limited to:

- Trade name
- Rationale for the origin of prescription: Whether it was a prophylactic^{a*} medication? Prophylactic medications will be recorded in the Action Taken section of the AE collection tables.
- Medication category (1, 2, or 3)
- Start and stop dates

^a Medication(s) prescribed for preventing AE occurrence (e.g. paracetamol to reduce the risk of fever)

Dosage and administration route, homeopathic medication, will not be recorded.

If the subject has received medications other than those listed in Categories 1, 2, and 3, the detailed information will be collected in the source documents only.

Medications given to treat an AE will be captured in the “Action Taken” section of the AE CRB only. No details will be recorded in the concomitant medication CRB unless the medication(s) received belongs to one of the prelisted categories.

7 Management of Samples

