5.2.2 Per-Protocol Analysis Set

The PPAS is a subset of the FAS. Two PPASs will be defined (PPAS1 for D06 and PPAS2 for D30). The subjects presenting with at least 1 of the following relevant protocol deviations will be excluded from the PPAS1 or PPAS2 as applicable:

- Subject did not meet all protocol-specified inclusion criteria or met at least 1 of the protocol-specified exclusion criteria
- Subject did not receive vaccine(s)
- Subject received a vaccine other than the one that he / she was randomized to receive
- Preparation and / or administration of vaccine was not done as per-protocol
- Subject did not receive vaccine in the proper time window
- Subject did not provide a post-dose serology sample in the proper time window or a post-dose serology sample was not drawn
- Subject received a protocol-prohibited Category 2 or Category 3 therapy / medication / vaccine
- Subject had other protocol violation that affected the subject's immune response, as determined by the clinical team prior to locking the database.

In addition to the reasons listed above, subjects will also be excluded from the PPAS if their serology sample did not produce a valid test result (ie, results for all antigens are missing).

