5.2.4 Populations Used in Analyses

All immunogenicity analyses will be performed on the PPAS1 or PPAS2. Additional immunogenicity analyses will be performed for exploratory purposes on the FAS1 or FAS2, according to randomized or assigned group. Antibody persistence analyses will be performed on the FAS3.

All safety analyses will be performed on the SafAS. Subjects will be analyzed according to the vaccine they actually received.

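### FAS3, the set for antibody persistence, keeps subjects with a pre-D0 deviation that can alter the D0 titer, and no D0-based per-protocol counterpart is defined

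*SAP*

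**What the plan says.** The protocol has no FAS3. Protocol 12.1 and 12.2.4 place every immunogenicity analysis on the per-protocol sets and treat the full analysis sets as exploratory.

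The SAP adds FAS3 and discloses this in section 5.7. Its definition in 5.2.1.2 has a single condition: "The FAS3 is defined as a subset of subjects who had a valid pre-vaccination serology result for antibody persistence analyses". Section 5.2.4 then says "Antibody persistence analyses will be performed on the FAS3". The same section still opens with "All immunogenicity analyses will be performed on the PPAS1 or PPAS2", so the two sentences overlap.

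Eligibility violators are removed only from the per-protocol sets. SAP 5.2.2 lists among the grounds for removal "Subject did not meet all protocol-specified inclusion criteria or met at least 1 of the protocol-specified exclusion criteria". SAP 4.4.3.5 states how prohibited products affect PPAS1 and PPAS2 and does not mention FAS3.

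Two exclusion criteria in Protocol 5.2.5 bear directly on the D0 titer. Criterion 5 is "Receipt of any meningococcal vaccine including a licensed or investigational MenACWY vaccine or MenB vaccine since participation in study MET50 or MET43". Criterion 19 is "Receipt of oral or injectable antibiotic therapy within 72 hours prior to the first blood draw". For systemic antibiotics, Protocol 6.7 gives the reason: "as they may interfere with bioassays used for antibody testing when taken before a blood draw".

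One exclusion specific to persistence exists, in SAP 5.1.3.2: Menveo-primed subjects from outside MET50 do not contribute. That rule concerns the source of priming, not protocol deviations.

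**The concern.** The quantity of interest is the titer 3 to 6 years after one priming dose. A subject who had a second MenACWY dose in between does not supply it, because the D0 titer then reflects the later dose.

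Such doses are plausible in this population. Protocol 1.2.1.4 reports that the US advisory committee "approved updated recommendations to include a booster dose of MCV4 at age 16 years for adolescents previously vaccinated at 11 to 12 years of age". MET50 subjects were 10 to 17 years old at priming (Protocol 1.2.1.1), so part of the cohort passed 16 before entering MET59. The Category 2 window for other vaccines in SAP 4.4.3.5 reaches back only 28 days. An older intervening dose is therefore caught through the eligibility exclusion, which FAS3 does not apply.

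The usual reason for keeping deviators in a full analysis set is weak here. D0 titers are taken before any study vaccine, so keeping deviators preserves no effect of MET59 randomization. The MenACYW-primed versus Menveo-primed contrast is also not randomized in MET59, since Group 2 is assigned (Protocol 6.5).

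At stake are the descriptive results for Secondary Objectives 3 and 4. If intervening doses are more common in one priming group, the between-vaccine GMTR is biased as well.

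**Working it through.** The plan states no figure on this point, so the check compares the sets and then illustrates the size.

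**Comparison of the sets**

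| Condition | PPAS1 / PPAS2 | FAS3 |
|---|---|---|
| Valid D0 result | not itself listed | required |
| Post-dose sample in window | required | not required |
| Eligibility criteria met | required | not required |
| No prohibited Category 2 or 3 product | required | not required |

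Dropping the post-dose sample suits a D0 analysis. Dropping the last two rows has no such reason, and SAP 5.7 gives none.

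**Size, under assumptions**

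The documents give neither the deviation rate nor the D0 titers. Assume that a fraction f of FAS3 had an intervening MenACWY dose and that their D0 titers are R times what they would otherwise be.

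- *GMT.* The mean log titer rises by f × log R, so the GMT is multiplied by R^f.
- *Paired ratio.* The MET50 D30 titer predates the intervening dose, so the ratio of MET59 D0 to MET50 D30 is also multiplied by R^f.
- *Between-vaccine GMTR.* With fractions f1 and f2 in the two priming groups and the same R, the factor is R^(f1 − f2). It equals R^f if only one group is affected.
- *Seroprotection.* If all deviators reach 1:8 or more, a true rate p rises by f × (1 − p).

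GMT factor R^f:

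| R | f = 1% | f = 3% | f = 5% |
|---|---|---|---|
| 8 | 1.021 | 1.064 | 1.110 |
| 16 | 1.028 | 1.087 | 1.149 |
| 64 | 1.042 | 1.133 | 1.231 |

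Rise in seroprotection, in percentage points:

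| True rate p | f = 1% | f = 5% |
|---|---|---|
| 80% | 0.01 × 0.20 = 0.2 | 0.05 × 0.20 = 1.0 |
| 60% | 0.01 × 0.40 = 0.4 | 0.05 × 0.40 = 2.0 |
| 40% | 0.01 × 0.60 = 0.6 | 0.05 × 0.60 = 3.0 |

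For scale, the planned MenACYW-primed total is 200 + 100 + 100 = 400. One percent of that is 4 subjects and 5% is 20. The exact 95% confidence interval at n = 400 runs from 35.2% to 45.0% for an observed 40%, and from 75.7% to 83.8% for an observed 80%. The half-width is therefore about 4 to 5 points. Even at 5% deviators, the shift in seroprotection is smaller than the sampling error.

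**The case against.** **Screening should keep the number low.** Eligibility is checked before the D0 draw (Protocol 5.1.4). Where there is a separate primary physician, the site should ask that physician to verify previous vaccines (Protocol 5.2.5). This stands, and it is why the likely size is small. It does not remove the gap: consent, eligibility check, draw and vaccination are planned for one visit, so a vaccination record can arrive afterwards.

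**Deviator-free D0 results are already planned.** SAP 5.1.4 lists D0 GMTs and rates of titer at or above 1:8 on PPAS2, as subgroup output for a report appendix. This is a real but partial cross-check. PPAS2 requires a D30 sample, and that output includes neither the between-vaccine persistence GMTR nor the paired ratio. Reading the general per-protocol sentence in SAP 5.2.4 as also covering persistence would still impose the D30 requirement.

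**Keeping deviators in a full set is conventional, and the change is disclosed.** That is fair, and it supports keeping FAS3. It does not explain the absence of a per-protocol counterpart when the protocol made the per-protocol sets the main ones.

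**A reader might infer that every eligibility breach inflates persistence.** The documents do not support that.
- On antibiotics they say only that interference with the assay is possible. An upward effect would be an inference from the killing-based readout.
- Immunosuppression could lower titers.
- Criterion 5 also covers MenB vaccine, and nothing in the documents says that MenB raises A, C, Y or W titers.
- Criterion 6 is largely moot, because it concerns the Group 2 enrichment population and Menveo-primed subjects from outside MET50 are already left out of persistence. Only entrants from MET50 Group 4 might arguably remain.
- The influenza and routine-vaccine windows have no shown effect on a D0 meningococcal titer.

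**Conclusion.** The gap in the text is real. FAS3 applies no eligibility or prohibited-product exclusion, and the persistence analyses are assigned to it without a D0-based per-protocol counterpart. The case is clearest for an intervening MenACWY dose, which would push the GMT, the seroprotection rate and the paired ratio upward. For antibiotics the point is possible assay interference, with no stated direction.

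The size is unknown. The illustrated ranges rest entirely on assumed f and R, and the 5% end would mean about 20 of 400 MenACYW-primed subjects wrongly enrolled. If screening works, the effect is probably small.

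A reader might infer that the persistence results will be overstated, or that the trial's conclusions are at risk. Neither follows. The documents show no deviation rate, the secondary objectives are descriptive with no hypothesis tested (SAP 5.1.2.1), and the primary sufficiency tests are per-protocol analyses that FAS3 does not touch. This is an inexpensive improvement to the persistence results, not a flaw in the primary analysis.

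**What to change.** In SAP 5.2.1.2 and 5.2.4:

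1. Define a D0-based per-protocol persistence set: FAS3 minus subjects with a pre-D0 deviation that plausibly alters the A, C, Y or W titer at D0. Chiefly these are an intervening MenACWY vaccine, systemic antibiotics within 72 hours before the draw, immune globulin or blood products, immunosuppression, and meningococcal infection. Do not remove subjects for influenza vaccine, other routine vaccines or MenB vaccine alone. Do not require a D30 sample.
2. Flag these deviations at the data review before database lock.
3. Report the persistence GMTs, seroprotection rates, between-vaccine GMTR and paired MET59-D0 to MET50-D30 ratio (MET43 where applicable) on this set alongside unrestricted FAS3.
4. Reconcile the two sentences in SAP 5.2.4. Also correct the count in SAP 5.2, which announces five analysis sets but lists six.

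The cost is one derived flag, largely from deviations already reviewed for the per-protocol sets, one extra set of tables, and the loss of a few subjects from the restricted set.

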5.2.2 Per-Protocol Analysis Set

The PPAS is a subset of the FAS. Two PPASs will be defined (PPAS1 for D06 and PPAS2 for D30). The subjects presenting with at least 1 of the following relevant protocol deviations will be excluded from the PPAS1 or PPAS2 as applicable:

- Subject did not meet all protocol-specified inclusion criteria or met at least 1 of the protocol-specified exclusion criteria
- Subject did not receive vaccine(s)
- Subject received a vaccine other than the one that he / she was randomized to receive
- Preparation and / or administration of vaccine was not done as per-protocol
- Subject did not receive vaccine in the proper time window
- Subject did not provide a post-dose serology sample in the proper time window or a post-dose serology sample was not drawn
- Subject received a protocol-prohibited Category 2 or Category 3 therapy / medication / vaccine
- Subject had other protocol violation that affected the subject's immune response, as determined by the clinical team prior to locking the database.

In addition to the reasons listed above, subjects will also be excluded from the PPAS if their serology sample did not produce a valid test result (ie, results for all antigens are missing).

